## 6.2. Procedures

All procedures for the Screening and Study Period should be conducted per the [Schedule of Activities](#) and [Assessments](#).

- **Demographics:** Information such as date of birth, race, and gender will be collected.
- **Medical History:** Medical history will include confirmation by genetic testing of the diagnosis of DMD as obtained as reported from an appropriate regulated laboratory using a clinically validated genetic test (genetic testing is not provided by the sponsor). Results must confirm the presence of a mutation in the dystrophin gene(s) which is clinically consistent with the diagnosis of DMD. The mutation type will be reported.

- Medical history data from B5161002 will be reviewed for any significant medical histories and concurrent illnesses that required or are requiring specialist consultation or treatment.
- **Medication History:** Complete history will include all prescription or non-prescription drugs, and dietary and herbal supplements taken within 28 days prior to the planned first dose. Detailed information (dose, regimen) on glucocorticoid steroids will be collected.
- **Physical Examination:** including nose and throat mucosal exam.
- **Tanner Stage and Testicular volume.** If sexual maturity is reached during the study as confirmed by an assessment of Tanner Stage V, these assessments are no longer mandatory.
- **Height:** Height should be measured in the morning. If a subject is unable to stand safely, an estimated height can be calculated using the subject's ulnar length and the instructions provided in the functional assessment manual.
- **Weight:** The body weight is required to calculate the subject's dose. After the first dosing visit the subsequent doses may be calculated based on the current visit's weight or on the prior month's weight.
- **Vital signs:** Pre-dose supine blood pressure, pulse rate, respiratory rate, and temperature.
- **ECG:** Single 12-lead ECGs will be obtained.
- **Cardiac MRI (with or without gadolinium) or Echocardiogram**
- The modality used to monitor LVEF should be consistent throughout the study for each subject and should be the same modality used in Study B5161002,
- If cardiac MRI with gadolinium is used, the imaging may only be performed following all other imaging at the study visit.
- **Clinical laboratory testing:**
- **Fasting blood collection:** serum ferritin, serum iron, TIBC and % transferrin saturation.
- **Blood samples** for Biomarkers: Group 1 (fasting collection) & Group 2.
- **Blood samples** for hematology, chemistry, GGT, GLDH, PT, aPTT, creatine kinase, amylase and cardiac troponin I.
- **Blood sample** for hormones (LH, FSH, T4, TSH, androstenedione, testosterone). Blood collection for hormones should be done in the morning. If Tanner stage V is reached these samples are no longer mandatory.

- **Blood sample** for immunogenicity.
- **Urine sample** for urinalysis.
- **Blood Sample for PK:** Will be collected prior to dosing.
- **Fecal occult blood:** Fecal sample is to be collected at home up to 1 week prior to scheduled visit window.
- **Clinical Outcomes Assessments (COA)**
- **PODCI:** This questionnaire will be completed by the caregiver and if possible a self-report will be completed by the subject at the same visit (subject must be 11 years or older to complete). If a subject is unwilling to provide self-reported data, they can still participate in the study.
- **C-SSRS:** Children's Since Last Visit (Version 6/23/10) will be completed with the caregiver.
- **EQ-5D:** The **EQ-5D-3L** will be completed by the caregiver and if possible the **EQ-5D-Youth** will be completed by the subject at the same visit. These are new assessments introduced in this study and should be completed at screening and subsequent visits outlined in the [Schedule of Activities](#). If a subject is unwilling to provide self-reported data can still participate in the study.
- **HRU questionnaire:** This assessment will be completed by the caregiver. This is a new assessment introduced in this study and should be completed at screening and subsequent visits outlined in the [Schedule of Activities](#).
- **ZBI:** This assessment will be completed by the caregiver. This is a new assessment introduced in this study and should be completed at screening and subsequent visits outlined in the [Schedule of Activities](#).
- **WPAI:CG:** This assessment will be completed by the caregiver. This is a new assessment introduced in this study and should be completed at screening and subsequent visits outlined in the [Schedule of Activities](#).
- **Magnetic resonance imaging (MRI):** liver. Baseline/screening data will be obtained from Week 93 in the B5161002 study.
- **Fasting Dual-energy x-ray absorptiometry (DXA):** whole body and spine.
- **X-ray:** non-dominant hand and wrist. The same hand imaged in the B5161002 study should be imaged in the B5161004 study. If Tanner stage V is reached during the study these assessments are no longer mandatory.

- **Ambulatory Status:** Ambulatory status will be collected at screening and as an unscheduled procedure if there should be a change from the screening assessment during the study. Ambulation is defined as the ability to walk unassisted and without braces for at least 10 m.
- **Functional assessments:** In order to provide optimal testing conditions and consistency in endpoint measurements, the functional assessments, should be completed at *approximately* the same time of day. All functional assessments should be completed in the following order, PFTs, 4SC, NSAA, ROM, Strength, PUL, 6MWT. If loss of ambulation occurs, the 4SC, NSAA and 6MWT will not be completed.

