Study Week a		1	5	9	13	17	21	25	29	33	37	41	45	49
Study Day a		1	29	57	85	113	141	169	197	225	253	281	309	337
Visit Window a	Up to 42 days								± 3 days					

they can still participate in the study.

- n. Children will become eligible to complete the Adolescent self-report version of the PODCI when they turn 11 years of age at which time they should be asked to complete the PODCI Adolescent self-report version at indicated time points throughout the study. In addition, caregivers will continue to complete the PODCI Parent-report (2-10 years) version throughout the study. If a subject is unwilling to provide self-reported data they can still participate in the study.
- o. Ambulatory status will be recorded at the screening visit. Ambulation is defined as the ability to walk unassisted and without braces for at least 10 m. At subsequent visits if subject becomes non-ambulatory this should be recorded.
- p. If a loss of ambulation has occurred 4 Stair Climb, Northstar Ambulatory Assessment and 6MWT do not need to be completed. Please record date that ambulation was lost.
- q. Investigational product should be delivered in a 2 hour window ±30 minutes including the flush time. If a dosing visit cannot be conducted within the visit window, attempts should be made to bring the subject back for dosing as soon as possible; however the dosing **must not occur** within 2 weeks prior to the next scheduled dose. If the subject cannot return in this timeframe, the dose should be missed and the next visit should be conducted per the [Schedule of Activities](#).
- r. PK samples to be taken prior to dosing.

PF-06252616

B5161004

Final Protocol, 08 April 2016

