Visit Number a	Year 2,3,4 and Early Withdrawal												Early Withdrawal
	14 26, 38	15, 27, 39	16, 28, 40	17, 29, 41	18, 30, 42	19, 31, 43	20, 32, 44	21, 33, 45	22, 34, 46	23, 35, 47	24, 36, 48	25, 37, 49	
Study Week a	53, 101, 149	57, 105, 153	61, 109, 157	65, 113, 161	69 117, 165	73, 121, 169	77, 125, 173	81, 129, 177	85, 133, 181	89, 137, 185	93, 141, 189	97, 145, 193	
Study Day a	365, 701, 1037	393, 729, 1065	421, 757, 1093	449, 785, 1121	477, 813, 1149	505, 841, 1177	533, 869, 1205	561, 897, 1233	589, 925, 1261	617, 953, 1289	645, 981, 1317	673, 1009, 1345	
Visit Window	± 3 days												

reported data they can still participate in the study.

- m. Ambulatory status should be reviewed at each visit. Ambulation is defined as the ability to walk unassisted and without braces for at least 10 m. If a subject becomes non-ambulatory this should be recorded in the CRF.
- n. If a loss of ambulation has occurred 4 Stair Climb, Northstar Ambulatory Assessment and 6MWT do not need to be completed. Please record date that ambulation was lost.
- o. Investigational product should be delivered in a 2 hour window ±15 minutes including the flush time. If a dosing visit cannot be conducted within the visit window, attempts should be made to bring the subject back for dosing as soon as possible; however the dosing **must not occur** within 2 weeks prior to the next scheduled dose. If the subject cannot return in this timeframe, the dose should be missed and the next visit should be conducted per the [Schedule of Activities](#).
- p. PK samples to be taken prior to dosing.

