#### 1.2.2. Duchenne Muscular Dystrophy

DMD is the most frequently inherited neuromuscular disease, and predominantly affects boys. It is an X-linked muscular dystrophy caused by a mutation at Xp21 in the gene coding for the protein dystrophin (Bushby et al, 2010; Manzur et al, 2008) which is absent from the muscle of boys with DMD. DMD is the most severe of all muscular dystrophies and is characterized by skeletal and cardiac muscle degeneration. Boys with DMD are phenotypically unremarkable at birth; onset of symptoms usually occurs around two to three years of age. Most boys lose the ability to walk between the ages of 10 and 14 (Lamperti & Moggio, 2010). Progressive cardiac problems manifest in the second decade.

There is no approved treatment that can stop or reverse the progression of DMD. Glucocorticoid therapy, although not specifically approved for use in DMD, is the only pharmacotherapy that has been demonstrated to ameliorate symptoms in patients with DMD,

irrespective of underlying mutation, and is currently the standard of care. Although glucocorticoids may improve muscle strength for a period of time and delay the loss of ambulation, (Mendell et al, 1989; Bonifati et al, 2000), chronic use is associated with well-known adverse events such as weight gain and broad hypothalamic-pituitary-adrenal axis effects which eventually lead to the discontinuation of treatment, often in the teenage years.

Additional disease management consists primarily of supportive care which ranges from physical therapy to maximize function and minimize muscle contractures, to orthotics, tendon release surgery (which provides temporary benefit as contractures will redevelop), use of wheel chair (usually by age 12), surgical correction of scoliosis and use of respiratory care including various forms of assisted ventilation (including tracheotomy). Respiratory infections may be treated with antibiotics. Death from pneumonia or cardiac involvement in late teens or early twenties is commonly observed in these patients (Manzur et al, 2008).

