### **1.3. Clinical Experience with PF-06252616**

The clinical program for PF-06252616 was initiated in June 2012 with a Phase 1 first-in-human (FIH), randomized, double-blind (sponsor and pharmacist unblinded), placebo-controlled study (B5161001) evaluating the safety, tolerability, pharmacokinetic, pharmacodynamic, and pharmacologic (anabolic) effects of escalating single doses of PF-06252616 in healthy adult subjects. The study is complete with 73 subjects enrolled at a single site. Single doses of 1, 3, 10, 20, and 40 mg/kg administered by the intravenous (IV) route and 3 mg/kg administered by the subcutaneous route, or placebo were studied. In addition, a repeat IV administration of PF-06252616 10 mg/kg at 2 week intervals over a 28-day treatment period was investigated. Safety was demonstrated at all dose levels and there were no dose-related trends in frequency of reported treatment-emergent adverse events (TEAEs).

The Protocol B5161002 is the first-in-patient (FIP) study with PF-06252616. This Phase 2 randomized, 2-period, double blind, placebo-controlled, multiple-ascending dose study aims to provide initial clinical assessment of the safety, efficacy, PK, and PD of PF-06252616

following repeat IV doses in ambulatory boys with DMD. Additionally, it aims to demonstrate the efficacy of treatment over 3 escalated IV dose levels of PF-06252616 based on an observed mean change from baseline on function 4SC as compared to placebo following 49 weeks of treatment. The study is ongoing and plans to enroll approximately 105 eligible subjects who will be randomly assigned to 1 of 3 sequence groups and receive placebo or investigational product PF-06252616 at 3 escalating dose levels of 5 mg/kg IV, 20 mg/kg IV, and 40 mg/kg IV administered every 4 weeks for approximately 96 weeks (2 treatment periods of approximately 48 weeks each).

Complete information for this compound may be found in the Single Reference Safety Document (SRSD), which for this study is the [Investigator's Brochure \(IB\)](#).

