## **2.2.2. Secondary endpoints**

### **2.2.2.1. Efficacy**

- Mean change from baseline following up to 4 years of treatment in the following functional assessment tests PFTs (to include FVC, FEV1 and PEFR), 4SC, NSAA, PUL, ROM and 6MWD.
- Mean change from baseline in muscle strength measured by myometry following up to 4 years of treatment.

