### **9.3. Efficacy Analysis**

#### **9.3.1. Analysis of efficacy and PD endpoints**

Baseline values, change from baseline to last visit in PFTs, 4SC, NSAA, PUL, 6MWD, muscle strength by myometry and lean body mass by DXA will be described based on summary statistics including minimum, median, mean, maximum, and standard deviation. Change from baseline may also be assessed for any or all intermediate visits.

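### Loss of ambulation ends 4SC, NSAA and 6MWT, yet the protocol summarises them as change from baseline to last visit; taken as written, this understates long-term decline in these exploratory secondary endpoints.

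*Protocol*

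**What the plan says.** **Collection.** Section 6.2 is categorical: "If loss of ambulation occurs, the 4SC, NSAA and 6MWT will not be completed". The Schedule of Activities footnotes are permissive: "If a loss of ambulation has occurred 4 Stair Climb, Northstar Ambulatory Assessment and 6MWT do not need to be completed". Sections 7.8, 7.8.2, 7.8.3 and 7.8.7 likewise allow omission for a non-ambulatory boy. Ambulatory status is followed throughout, and the footnotes ask for the date of loss: "Please record date that ambulation was lost". Section 7.8 asks for it where possible.

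**Endpoint and summary.** Section 2.2.2.1 defines the secondary efficacy endpoint as "Mean change from baseline following up to 4 years of treatment in the following functional assessment tests", and the tests it lists include 4SC, NSAA and 6MWD. Section 9.3.1 covers "Baseline values, change from baseline to last visit in PFTs, 4SC, NSAA, PUL, 6MWD, muscle strength by myometry and lean body mass by DXA", described by "summary statistics including minimum, median, mean, maximum, and standard deviation"; intermediate visits are optional. Neither section mentions loss of ambulation or says what last visit means for a boy no longer tested.

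**Expected frequency.** Section 1.2.2 states: "Most boys lose the ability to walk between the ages of 10 and 14". Section 1.3 describes the parent study as treatment "following repeat IV doses in ambulatory boys with DMD", lasting about 96 weeks. The extension adds up to 4 years.

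**Status.** Safety is primary (2.1.1), all analyses are exploratory (section 9), and there is no placebo comparator (3.1).

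**The concern.** Losing the ability to walk is the worst result these three tests can register, and it is also the event that stops them. The value is therefore missing because of the outcome being measured. The wording of 9.3.1 leaves two literal readings. Either the boy has no value at his last study visit and leaves the summary, or his last available test counts as his last visit and he stays at a distance, score or time that he could still achieve. For 4SC the problem is sharper, because 7.8.2 defines it as a time in seconds and no finite time exists for a boy who cannot climb.

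Section 1.5 gives maintenance of effect over up to 4 years as one purpose of the study. Without a comparator, nothing in an average that omits or freezes the weakest boys would reveal the selection, and a slower apparent decline could be read as maintenance.

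**Working it through.** The protocol gives no figure to reproduce: the sample size of about 105 is a cap from the parent study, with no power calculation. The check is therefore on direction and rough size.

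**Direction.** Let p be the share who lose ambulation, c the mean change in boys still tested, B the mean baseline of those who lost it, and M the mean of their last tests. With loss scored as 0 m:
- all-boys mean change = (1 - p) × c - p × B;
- gap if only tested boys are averaged = p × (c + B), which is positive unless the tested boys decline by at least B;
- gap if the last test is kept = p × M, which is positive by construction.

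**Inputs from the protocol.** Section 7.8.7 gives one-year 6MWD changes of -23 to -59 m with SD 81 to 90 m. I use values within these ranges: (-23 - 59)/2 = -41 m and SD 85 m. Week 193 is Day 1345, so (1345 - 1)/365.25 = 3.68 years. The protocol's only ambulation distance is 10 m walked unassisted and without braces.

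**Assumptions.** Baseline 6MWD has mean 330 m, SD 80 m and a minimum of 120 m. Loss is permanent once the simulated distance falls below 10 m; applying the 10 m definition to the 6MWD scale is itself an assumption. Of the one-year variance, 30% is a persistent boy-specific slope and the rest a random walk. Tests fall at Weeks 13, 25, 49, 69, 97, 117, 145, 165 and 193.

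**Result at Week 193 (Monte Carlo).** p = 0.246, M = 58 m.

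| How boys with loss are handled | Mean 6MWD change |
|---|---|
| Scored 0 m | -122 m |
| Last test kept | -108 m |
| Only tested boys averaged | -66 m |

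- Last test kept: 122 - 108 = 14 m hidden, agreeing with 0.246 × 58 = 14 m. If boys with loss are credited with 10 m instead of 0, the gap falls by 0.246 × 10 = 2.5 m, to about 12 m.
- Tested only: 122 - 66 = 56 m hidden, or 56 - 2.5, about 54 m, with the 10 m credit.
- As shares of the 122 m decline: 14/122 = 11% and 56/122 = 46%.
- Medians in the same order are -150, -138 and -83 m, so the median hides 12 m and 67 m.

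**Sensitivity.** Thresholds of 50 and 100 m, which are not in the protocol, give 31% and 39% with loss. Against 0 m the last-test gap becomes 124 - 95 = 29 m and 132 - 76 = 56 m; the tested-only gap becomes 124 - 47 = 77 m and 132 - 22 = 110 m. A simpler model (100 m threshold, loss scored 0 m, baselines 300 to 400 m, four years) gives tested-only gaps of 36 to 112 m. The sign is the same throughout.

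**Is 25% plausible?** Take age at loss as normal around 12, with 60 to 90% of boys between 10 and 14, so SD = 2/z((1 + share)/2). Among boys still walking at entry, loss within 3.68 years is 14-28% for an assumed entry age of 7, 40-42% for 8 and 57-71% for 9. Section 1.2.2 says that glucocorticoids may delay loss, which would lower these figures.

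**NSAA and 4SC, last test kept, 25% with loss.** An assumed last NSAA of 4 to 10 points (maximum 17 × 2 = 34) gives 0.25 × 4 = 1.0 to 0.25 × 10 = 2.5 points. An assumed last 4SC of 20 to 8 s is 4/20 = 0.2 to 4/8 = 0.5 stairs/s, which gives 0.05 to 0.125 stairs/s.

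**The case against.** The strongest reply is that this belongs in the SAP. Handling of values missing after an event is commonly settled there, section 9 leaves even the baseline definition to it, and the list of statistics in 9.3.1 is open-ended. Nothing is lost for most remedies, because ambulatory status and the date of loss are collected. This stands to the extent that no one can say a rule is absent. It does not remove the point: the protocol itself has chosen the endpoint, the time point and the statistics, and these do not fit its own rule for stopping the tests.

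Second, loss of ambulation is not invisible. Section 8.6.1 requires it to be captured as an AE and provides aggregate and quarterly E-DMC review; TEAE incidence is a primary endpoint (2.2.1.1) and is summarised (9.2). A reader might infer that the protocol would conceal how many boys stop walking. It would not. What is missing is the link to the efficacy summaries.

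Third, understatement presumes interest in all boys. A summary restricted to boys while they can walk answers a legitimate but different question, provided it is labelled as such. Floor scores and 4SC velocity are conventions, and they mix inability with measured performance.

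Fourth, a reader might take the larger gaps as the expected bias. The documents do not support that: those gaps need assumed thresholds of 50 to 100 m or the tested-only reading, whereas 9.3.1 refers to last visit. At 10 m with the last test kept, the gap is modest.

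**Conclusion.** The point holds in a limited form. As written, 2.2.2.1 and 9.3.1 give a picture of 4SC, NSAA and 6MWD that is too favourable for the whole group, unless the SAP assigns a value after loss of ambulation. The direction depends only on counting loss as worse than the last walking result.

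The size cannot be settled from the protocol. The central illustration hides about 12-14 m of mean 6MWD decline with the last test kept and about 54-56 m with tested boys only. It rests on the assumed baseline, a constant yearly decline, the variance split and the use of 10 m as the 6MWD threshold.

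It would go too far to infer that the study's main conclusions are biased. Safety is primary, the efficacy analyses are descriptive with no test or decision rule, and PFTs, PUL and strength are not on the list of tests dropped at loss. The point is worth fixing because the flattering direction coincides with the stated interest in maintenance of effect and the correction is cheap.

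**What to change.** Add to section 9.3.1, as descriptive efficacy summaries:

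1. The number of boys losing ambulation and the time to loss (Kaplan-Meier), using the recorded date or, where it is missing, the interval between visits.
2. Each ambulatory-test summary labelled as applying while ambulatory, with the number tested and the number with loss at each visit, and a statement of what last visit means for a boy no longer tested.
3. A sensitivity summary counting loss as the worst outcome: for example 0 for 6MWD and NSAA, or a rank-based or median summary, and 4SC as velocity (4 stairs divided by seconds) with 0 for unable. State that these values are a convention.

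If the SAP already has such a rule, a cross-reference in 9.3.1 would cover that part.

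Separately, reconcile section 6.2 with the Schedule footnotes and sections 7.8, 7.8.2, 7.8.3 and 7.8.7 on whether the three tests are done after loss, since sites could differ in whom they test. Also reconcile 7.8.4, which lets ROM be omitted after loss, with 6.2 and the footnotes, which do not list it. ROM is not in the 9.3.1 list, so that mismatch does not affect the bias described here.

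The cost is a few sentences and some programming, with no new data. The downside is that a floor value blends inability with measured performance, which is why the while-ambulatory and worst-outcome summaries should appear side by side.

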### 6.3. Subject Withdrawal

Subjects may withdraw from the study at any time at their own request, or they may be withdrawn at any time at the discretion of the investigator or sponsor for safety or behavioral reasons, or the inability of the subject/caregiver to comply with the protocol-required schedule of study visits or procedures at a given study site. Subjects may be withdrawn from the OLE study should the parent study, B5161002 fail to meet its planned study objectives, is terminated early for other reasons (eg, sponsor decision) or the drug is commercialized. If a subject does not return for a scheduled visit, every effort should be made to contact the subject. All attempts to contact the subject and information received during contact attempts must be documented in the subject's medical records. In any circumstance, every effort should be made to document subject outcome, if possible. The investigator should inquire about the reason for withdrawal, request that the subject to return for a final visit, if applicable, and follow-up with the subject regarding any unresolved AEs.

If the subject withdraws from the study and also withdraws consent for disclosure of future information, no further evaluations should be performed and no additional data should be collected. The sponsor may retain and continue to use any data collected before such withdrawal of consent.

In the event of clinically important treatment-emergent suicidal ideation or suicidal behavior, the subject will be withdrawn from the study and will receive the appropriate medical care. The Investigator will follow up until the subject's condition has stabilized. Additionally, a risk assessment or evaluation of suicide risk will be completed by a child and adolescent mental health provider as part of the psychiatric evaluation and assessment of subject safety. Refer to [Section 7.2.7](#).

Clinically important suicidality includes but is not limited to:

- a. Suicidal behavior (with or without intent of suicide or serious self-harm).
- b. Determination of “yes” on question 4 (Active Suicidal Ideation with Some Intent or Act, Without Specific Plan) for the Suicidal Ideation section of the C-SSRS.

- c. Determination of “yes” on question 5 (Active Suicidal Ideation with Specific Plan and Intent) for the Suicidal Ideation section of the C-SSRS.
- d. Determination of “yes” on the question of Actual Attempt, Interrupted Attempt, Aborted Attempt, or Preparatory Acts or Behavior for Suicidal Behavior section of C-SSRS.
- e. Acute suicidality to such a degree that precaution against suicide must be exercised.

At the time of withdrawal, procedures outlined in the early withdrawal visit should be performed as detailed in the [Schedule of Activities](#) and [Assessments](#).

